7.4.5.2 Analysis

The number of subjects with events and subjects with censored observations will be presented by treatment group.

A Kaplan-Meier plot will be produced showing all five treatment arms and p-values.

The treatment effect will be estimated using a stratified Cox proportional hazard model (displaying hazard ratios and 95% CI), stratified by OCS and mSLEDAI-2K (from IXRS). Hazard ratios and 95% CI will also be displayed in the Kaplan-Meier plot.

```
* KM;
proc lifetest;
  strata treatment;
  id subjid;
  time time*censor(1);
  ods select productlimitestimates quartiles;
run;

* cox proportional hazard model;
proc phreg;
  class treatment (ref="placebo");
  model time*censor(1) = treatment / ties=exact rl;
  strata ocs sledai_sc;
  ods select ParameterEstimates;
run;
```

The analysis will be conducted for data collected during TP1 up to both Month 6 and EOT.

7.4.6 Time to first flare up to Month 6

7.4.6.1 Variables

Variables for the endpoint ‘time to first flare from baseline to Month 6’ are derived exactly in the same way as in the previous section, with the only difference that all flares instead of only severe flares are included. Variables are derived up to EOT (during TP1) and up to Month 6.

7.4.6.2 Analysis

The Cox proportional hazards model will be repeated as described in Section 7.4.5.2 for data collected during TP1 up to both Month 6 and EOT.

7.4.7 Change from baseline to Month 6 in PGA score

7.4.7.1 Variables

The absolute change from baseline to Month 6 in PGA score is derived as:

$$\text{Change in PGA} = \text{PGA score at Month 6} - \text{PGA score at baseline.}$$

In the event of missing values at one of the assessments, the variable is set to missing.

7.4.7.2 Analysis

An MMRM model will be used to analyze this endpoint including all monthly visits (similar to primary efficacy analysis in Section 7.2.5).

The following fixed effects will be included in the model: PGA baseline value, the two stratification factors (OCS and mSLEDAI-2K from IXRS), treatment group, month, treatment group by month interaction and PGA baseline value by month interaction.

7.5 Exploratory endpoints

All exploratory endpoints will be summarized descriptively and listed using the FAS or FAS-TP2 unless otherwise stated.

Additional analyses for the exploratory endpoints are described in the sections below.

Exploratory endpoints will be analyzed from baseline up to a maximum of 12 months on all available assessments according to 2 Groups:

- Group 1: All randomized subjects, for whom baseline is defined as the last available measurement before the start of randomized treatment in TP1.
- Group 2: Subjects re-randomized at Month 6, for whom baseline is defined as the last available measurement before the start of re-randomized treatment in TP2.

A time window approach will be applied to the endpoints where data will be analyzed at protocol-mandated visits [as defined in Section 5.4.4].

The display of treatment groups in the summary tables is as defined in Section 5.4.3. Group 1 will be analyzed based on 5 treatment groups (Placebo, 0.5, 1, 2, 4 mg), whereas Group 2 will be analyzed based on 6 treatment groups (Placebo, 0.5, 1, 2, 4 mg / 2 mg and 4 mg / placebo).

7.5.1 Sustained mSLEDAI-2K response defined as a reduction of at least [REDACTED]
[REDACTED]
[REDACTED]
[REDACTED]

7.5.1.1 Variables

A binary response variable is derived for this endpoint. The following criteria apply for a responder (1):

- Subject must have at least [REDACTED] mSLEDAI-2K assessments [REDACTED]
[REDACTED]
- Subject must have a reduction of the mSLEDAI-2K of at least [REDACTED]
[REDACTED]
- Subject must have a reduction of the mSLEDAI-2K of at least [REDACTED]
[REDACTED]

[REDACTED]
[REDACTED]
[REDACTED]
[REDACTED]

7.5.1.2 Analysis

This endpoint will only be analyzed for Group 1 using the FAS with a logistic regression model.

The logistic regression model will include the treatment group [as defined in Section 5.4.3.1] and will be stratified by the OCS and mSLEDAI-2K stratification variables (from IXRS).

The estimates of the ORs between each cenerimod dose group and placebo will be reported with their 95% CIs. In addition, the proportion of responders will be reported by treatment group.

7.5.2 Change from baseline to each post-baseline assessment up to Month 12 in mSLEDAI-2K score

7.5.2.1 Variables

Group 1

The variable is derived as defined in the primary endpoint Section 7.2.1, for each visit up to Month 12.

Group 2

The variable is derived as defined in the primary endpoint Section 7.2.1 for each visit from Month 6 up to Month 12 based on the TP2 baseline value for all subjects in FAS-TP2.

7.5.2.2 Analysis

Group 1

An MMRM analysis will be performed as described in Section 7.2.5, including visits up to Month 12 using 5 treatment groups as defined in Section 5.4.3.3.

Group 2

An MMRM analysis will be performed similar to the one described in Section 7.2.5, but only including data from Month 7 up to Month 12 and from treatment groups *Cenerimod 2 mg / Ex-4 mg* and *Placebo / Ex-4 mg*. The model will include treatment group, month, TP2 baseline mSLEDAI-2K score, treatment group by month interaction and TP2 baseline mSLEDAI-2K score by month interaction as fixed effects.

All other aspects of the model are as described in Section 7.2.5.

7.5.3 Response at each post-baseline assessment on the mSLEDAI-2K

7.5.3.1 Variables

Group 1

The variable is derived as in Section 7.4.1.1 for each visit up to Month 12.

Group 2

The variable is derived as in Section 7.4.1.1 for each visit from Month 6 up to Month 12 based on the TP2 baseline value for all subjects in FAS-TP2.

7.5.3.2 Analysis

Group 1

A repeated measurements GLMM model for binary response variables will be performed as described in Section 7.3.1.5 based on 5 treatment groups as described in Section 5.4.3.3.

Group 2

A repeated measurements GLMM model for binary response variables will be performed as described in Section 7.3.1.5. The model will be fitted including data from Month 7 up

to Month 12 and from treatment groups *Cenerimod 2 mg / Ex-4 mg* and *Placebo / Ex-4 mg*. The model will include treatment group, month, TP2 baseline mSLEDAI-2K score, treatment group by month interaction and TP2 baseline mSLEDAI-2K score by month interaction as fixed effects.

All other aspects of the model are as described in Section 7.3.1.5.

7.5.4 Response (no worsening and improvement) at each post-baseline assessment on BILAG-2004 disease activity index

7.5.4.1 Variables

Group 1

The variable is derived as defined in Section 7.4.2 for each visit up to Month 12.

Group 2

The variable is derived as defined in Section 7.4.2 for each visit from Month 6 up to Month 12 based on the TP2 baseline value for all subjects in FAS-TP2.

7.5.4.2 Analysis

Group 1

A repeated measurements GLMM model for binary response variables will be performed as described in Section 7.3.1.5 based on 5 treatment groups as described in Section 5.4.3.3.

Group 2

A repeated measurements GLMM model for binary response variables will be performed, as described in Section 7.3.1.5. The model will be fitted including data from Month 7 up to Month 12 and from treatment groups *Cenerimod 2 mg / Ex-4 mg* and *Placebo / Ex-4 mg*. The model will include treatment group, month and treatment group by month interaction as fixed effects.

All other aspects of the model are as described in Section 7.3.1.5.

7.5.5 Response at each post-baseline assessment on SRI-4, -5, -6, -7, -8

7.5.5.1 Variables

Group 1

The variables are derived as defined in Sections 7.3.1.2 and 7.4.3.1 for each visit from Month 1 up to Month 12.

Group 2

The variables are derived as defined in Sections 7.3.1.2 and 7.4.3.1 for each visit from Month 6 up to Month 12 based on the TP2 baseline value for all subjects in FAS-TP2.

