2 STUDY DESIGN AND FLOW

2.1 Study design

This is a Phase 2b, multicenter, randomized, double-blind, placebo-controlled, parallel group study to evaluate the efficacy, safety, and tolerability of cenerimod in subjects with moderate to severe SLE.

Approximately 325 adult subjects with SLE will be randomized in a 1:1:1:1:1 ratio to placebo, 0.5, 1, 2, or 4 mg once daily of cenerimod, in addition to background SLE therapy.

Once randomized, all subjects will enter a 6-month double-blind study treatment period defined as Treatment Period 1 (TP1).

Subjects randomized to, and still receiving, placebo, 0.5, 1, or 2 mg at Month 6 will continue their study treatment up to an additional maximum of 6 months in Treatment Period 2 (TP2), for a total maximum of 12 months.

Subjects randomized to the 4 mg arm will receive study treatment at this dose for a maximum of 6 months in TP1. Afterwards, subjects in this group, still receiving this dose

at Month 6, will be re-randomized in a 1:1 ratio to placebo or cenerimod 2 mg to enter TP2 and will continue for a total maximum of 12 months

Subjects who discontinue treatment in TP1 will continue study FU, performing study assessments, up to maximum duration of 12 months.

At EOT, subjects will enter a 6-month FU period (4-month before protocol Version 5).

Treatment allocation is stratified by dose of OCS at Randomization (two strata: < 7.5 mg/day or ≥ 7.5 mg/day prednisone or equivalent), and by disease activity at Screening (with two strata: mSLEDAI-2K < 10 or ≥ 10).

The study will be conducted at approximately 180 sites in 21 countries notably from the regions of Asia Pacific, Eastern Europe, Latin America, North America, and Western Europe.

No interim analysis is planned. There will be three study analyses: the Month-6 analysis, the Month-12 analysis and the final EOS analysis. Month-6 analysis will be performed when all randomized subjects have completed TP1 or discontinued the study. Month-12 analysis will be performed when all randomized subjects have completed TP2 or discontinued the study. Final EOS analysis will be performed when all randomized subjects have completed the post-treatment follow-up period or discontinued the study.

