3.3 Exploratory objectives

To explore the sustainability of the treatment effect, further objectives are assessed over a treatment period of up to 12 months:

- The effect of cenerimod 0.5, 1, 2 mg on disease activity, safety and tolerability, QoL, fatigue and SLE biomarkers.
- Starting from Month 6, the effects of dose reduction and withdrawal in subjects randomized to 4 mg who are re-randomized to either 2 mg or placebo.

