5.2 Baseline

- The **‘Baseline (TP1)’** value for **efficacy and safety analyses** is defined as the last non-missing value recorded prior to first study drug intake in TP1 for each endpoint and each subject individually. For subjects that were randomized but did not take any study drug, baseline (TP1) is defined as the last non-missing value recorded up to and including the day of Randomization.
- The **‘Baseline (TP2)’** value for **efficacy and safety analyses** is defined as the last non-missing value recorded up to and including the day of re-randomization for each endpoint and each subject individually. This baseline is only defined for subjects that have been re-randomized by IXRS.

For certain datasets/analyses an **‘intra-day baseline’** is derived (e.g., ECG, vital signs). This intra-day baseline is defined as the last non-missing assessment prior to study drug intake on the corresponding day. If there is no pre-dose assessment on the day (by time and date), then the intra-day baseline is considered to be missing. The intra-day baseline is calculated for parameters that are part of the hourly measurements on the day of first study drug intake (in TP1) and the day of first study drug intake of a re-initiated subject (in TP1).

For datasets where multiple measurements exist for the selection of the baseline assessment, the definition(s) is/are provided in the corresponding sections (e.g., spirometry or ECG data).

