7.3.1.2 Variables

The three variables are defined as follows:

mSLEDAI-2K Responder

The absolute change of the mSLEDAI-2K from baseline to Month 6 (using time window approach) is defined as:

$$\text{Change in mSLEDAI-2K} = \text{mSLEDAI-2K score at Month 6} - \text{mSLEDAI-2K score at baseline.}$$

Subjects with a reduction from baseline to Month 6 of ≥ 4 are considered to be responders (Responder = 1), subjects with a reduction of < 4 or an increase are considered to be non-responders (Responder = 0).

BILAG-2004 Responder

A responder (1) is defined as having no new BILAG A organ domain score and at most one new BILAG B organ domain score assessed for the nine body systems. A responder can only be assessed if the full information of all body systems is available.

Non-responders (0) are defined as having one or more new BILAG A organ domain scores or at least two or more BILAG B organ domain scores. In the event of incomplete data in at least one of the body systems, but sufficient information to fulfill the non-response criteria, the subject will be considered to be a non-responder.

Subjects that fit none of the above criteria will be assigned a missing value.

PGA Responder

The absolute change of PGA from baseline to Month 6 is defined as follows:

$$\text{Change of PGA} = \text{PGA value at Month 6} - \text{PGA value at baseline.}$$

A responder (1) is a subject with an increase of ≤ 0.3 compared to baseline. A non-responder (0) is defined as having an increase of > 0.3 compared to baseline. Subjects with missing data either at baseline or Month 6 will be assigned a missing value.

Composite endpoint

A responder (1) for the endpoint SRI-4 response at Month 6 is defined as a responder of all three variables, as defined above. If at least one of the three variables indicate non-response, the subject is considered to be a non-responder (0). If at least one of the three variables is missing, the subject is assigned a missing value, unless at least one non-missing variables indicates non-response.

Data of this endpoint is derived for all monthly post-baseline visits up to Month 6.

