7.4.3 Response at Month 6 on SRI-5, -6, -7, -8

7.4.3.1 Variables

The binary response variables of these endpoints are derived as described in Section 7.3.1.2 with a reduction in mSLEDAI-2K of 5, 6, 7 or 8, instead of a reduction of 4.

For SRI-X (X = 5, 6, 7 or 8) subjects with a baseline value of less than X will be excluded from the analysis.

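### The Group 2 responder endpoints count response from the Month 6 (TP2) baseline, so they measure further improvement and cannot show whether a response gained on 4 mg is kept or lost

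*SAP*

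**What the plan says.** SAP 3.3 sets an exploratory objective on whether the effect is sustained. From Month 6 it asks for "the effects of dose reduction and withdrawal in subjects randomized to 4 mg who are re-randomized to either 2 mg or placebo". SAP 2.1 supplies the design: subjects still on 4 mg at Month 6 "will be re-randomized in a 1:1 ratio to placebo or cenerimod 2 mg to enter TP2".

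The Group 2 responder variables are built as follows.

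- **Baseline.** SAP 5.2: the TP2 baseline "is defined as the last non-missing value recorded up to and including the day of re-randomization".
- **mSLEDAI-2K response.** SAP 7.5.3.1: "The variable is derived as in Section 7.4.1.1 for each visit from Month 6 up to Month 12", using the TP2 baseline. The rule it points to (7.4.1.1, then 7.3.1.2) requires a fall of at least 4 points.
- **SRI-4 to SRI-8.** SAP 7.5.5.1: derived under 7.3.1.2 and 7.4.3.1, "based on the TP2 baseline value for all subjects in FAS-TP2". Under 7.3.1.2, failing any one of the three components makes the composite a non-response.
- **Exclusion.** SAP 7.4.3.1, for SRI-X with X = 5 to 8: "subjects with a baseline value of less than X will be excluded from the analysis". No such exclusion is stated for SRI-4 or for mSLEDAI-2K response.
- **Models.** SAP 7.5.3.2 and 7.5.5.2 compare 2 mg/Ex-4 mg with placebo/Ex-4 mg at Months 7–12. The mSLEDAI-2K response model includes the TP2 baseline score; the SRI model does not.

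**The concern.** In a withdrawal comparison, the natural binary question is whether subjects who responded on 4 mg still respond after stepping down to 2 mg or switching to placebo. The Group 2 responder variables instead ask for another 4 to 8 points of improvement from a score that six months on 4 mg may already have lowered. Subjects with little room left to improve either count as failures throughout or leave the analysis. Among them, a subject who stays in low disease activity and one who relapses fully receive the same code. A table of these endpoints by re-randomized arm could easily be misread as evidence on whether response is maintained.

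**Working it through.** The plan states no sample size, power, response rate or Month 6 distribution for Group 2, so there is no figure to reproduce. The check is mainly one of logic.

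**1. Who can respond.** The score is a sum of weighted descriptors and cannot fall below 0 (SAP 6.8.3.3.1; the range 0 to 104 is used in 7.2.6.1.1). The largest possible fall from a TP2 baseline *s* is therefore *s*.

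| Endpoint | Fall needed | TP2 baselines that cannot reach it | Handling under the plan |
|---|---|---|---|
| mSLEDAI-2K response, SRI-4 | 4 | 0–3 | non-responder at every assessed visit |
| SRI-5 | 5 | 0–4 | excluded |
| SRI-6 | 6 | 0–5 | excluded |
| SRI-7 | 7 | 0–6 | excluded |
| SRI-8 | 8 | 0–7 | excluded |

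The BILAG and PGA components cannot alter an SRI-4 code once the mSLEDAI-2K component has failed. The TP2 baseline term in the mSLEDAI-2K response model does not restore information on subjects who cannot respond.

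**2. Worked subject.** Take a TP1 baseline of 10 and a Month 6 score of 2 (mSLEDAI-2K component, Months 7–12).

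| Scores, Months 7–12 | Coded from TP2 baseline | Coded from TP1 baseline | Change from TP2 baseline |
|---|---|---|---|
| 2, 2, 2, 2, 2, 2 | 0,0,0,0,0,0 | 1,1,1,1,1,1 | 0 throughout |
| 4, 6, 8, 10, 10, 10 | 0,0,0,0,0,0 | 1,1,0,0,0,0 | +2, +4, +6, +8, +8, +8 |

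The TP2 coding cannot tell the two courses apart. The TP1 coding and the change score both can.

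**3. Numbers available.** SAP 2.1: "Approximately 325 adult subjects with SLE will be randomized in a 1:1:1:1:1 ratio". That gives 325/5 = 65 on 4 mg and 65/2 = 32.5, so at most about 32 per re-randomized arm.

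**4. Share affected (assumed distribution).** Treat the Month 6 score as a normal variable rounded to whole numbers, with negative values set to 0. Then P(score < 4) = Φ((3.5 − mean)/SD) and P(score < 8) = Φ((7.5 − mean)/SD).

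| Mean / SD (assumed) | P(< 4) | P(< 8) |
|---|---|---|
| 5 / 3.5 | Φ(−0.429) = 0.33 | Φ(0.714) = 0.76 |
| 6 / 3.5 | Φ(−0.714) = 0.24 | Φ(0.429) = 0.67 |
| 6 / 4 | Φ(−0.625) = 0.27 | Φ(0.375) = 0.65 |
| 7 / 4 | Φ(−0.875) = 0.19 | Φ(0.125) = 0.55 |

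With 32.5 per arm, 19–33% is about 6 to 11 subjects per arm fixed as SRI-4 non-responders. Truncating the normal at 0, instead of flooring it, gives a somewhat lower 16–28% below 4. A weighted sum of descriptors is only roughly normal, so these are orders of magnitude.

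**5. Effect on the arm difference.** If a share *f* in each arm cannot respond, a difference *d* among those who can becomes (1 − *f*) × *d*. With assumed rates of 40% versus 20% (*d* = 20 points), *f* = 20% gives 0.8 × 20 = 16 points and *f* = 40% gives 0.6 × 20 = 12 points.

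**6. Is TP1-baseline response by re-randomized arm planned elsewhere?** Group 1 derives these endpoints from the TP1 baseline up to Month 12. SAP 7.5 gives Group 1 five treatment groups with 4 mg unsplit. SAP 7.5.3.2 and 7.5.5.2 give five groups but cite 5.4.3.3, which lists six with the ex-4 mg subjects split. The text does not settle whether the split will be shown.

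**The case against.** The strongest reply is that Group 2 does not rest on the responder endpoints. It also compares the two ex-4 mg arms on change in mSLEDAI-2K from the TP2 baseline (7.5.2.2), change in PGA (7.5.6.2), time to first severe flare (7.5.8.2) and time to first flare (7.5.9.2), and it tabulates flares (7.5.7.2). The relapsing subject above contributes +8 to the change analysis. This stands. A reader might infer that loss of effect after withdrawal goes unmeasured, or that the objective in 3.3 cannot be addressed; the documents support neither. The gap is confined to the binary endpoints.

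A reader might also infer bias between arms. None follows: the TP2 baseline precedes the re-randomized treatment, so fixed non-response and exclusion act on a pre-treatment value in both arms. The cost is lost sensitivity and a narrower population.

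Nor are the subjects affected simply those who did best on 4 mg. A fall from 6 to 3 leaves a subject unable to respond, whereas a fall from 20 to 8 does not.

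Part of the missing result may already be planned. On a six-group reading of Group 1, response against the TP1 baseline after Month 6 would be shown by re-randomized arm. That is possible but unresolved, and the unredacted text specifies no maintenance analysis among Month 6 responders.

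Finally, these endpoints are exploratory, lie outside the testing strategy in 7.1.1, and follow a Group 2 baseline that SAP 2.4.2 attributes to the protocol. That limits the severity and argues for adding to the planned version, not replacing it.

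**Conclusion.** The point holds for the Group 2 responder endpoints in 7.5.3 and 7.5.5. Fixed non-response at Month 6 scores of 0–3, and exclusion below X for SRI-5 to SRI-8, follow from the definitions without any assumption, given that 7.4.3.1 is read with the TP2 baseline as 7.5.5.1 directs. These endpoints score further improvement and are silent on maintenance.

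The share affected is not in the documents. The figures of 19–33% below 4 and 55–76% below 8 depend on the assumed Month 6 mean, SD and shape. The primary and secondary analyses are untouched, and the other Group 2 analyses still capture worsening. Severity is low: a cheap improvement to exploratory outputs.

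**What to change.** For 2 mg/Ex-4 mg versus placebo/Ex-4 mg, add to 7.5.3 and 7.5.5:

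- mSLEDAI-2K response and SRI-4 to SRI-8 against the TP1 baseline at each of Months 7–12, with the exclusion for a baseline below X applied to the TP1 baseline;
- maintenance of response at Months 7–12 among subjects who were responders at Month 6 against the TP1 baseline, with that status taken from assessments up to re-randomization so that the subset is defined before TP2 treatment.

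Keep the TP2-baseline responder variables as descriptive outputs, and leave the change and flare analyses as planned. Reconcile the Group 1 treatment groups across 7.5, 7.5.3.2, 7.5.5.2 and 5.4.3.3, so that TP1-baseline response after Month 6 is shown by re-randomized arm.

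The cost is a few more exploratory outputs from data already collected, alongside the protocol-defined version. The maintenance subset will be small. If 30%, 50% or 70% of about 32 per arm respond at Month 6 (assumed), it holds about 9, 16 or 22 per arm. With response kept in an assumed 80% versus 40%, power at a two-sided 5% level (normal approximation for two proportions) is about 0.40, 0.65 or 0.79. It should be reported as estimates with confidence intervals.

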7.5.5.2 Analysis

Group 1

A repeated measurements GLMM model for binary response variables will be performed as described in Section 7.3.1.5 based on 5 treatment groups as described in Section 5.4.3.3.

Group 2

A repeated measurements GLMM model for binary response variables will be performed, as described in Section 7.3.1.5. The model will be fitted including data from Month 7 up to Month 12 and from treatment groups *Cenerimod 2 mg / Ex-4 mg* and *Placebo / Ex-4 mg*. The model will include treatment group, month and treatment group by month interaction as fixed effects.

All other aspects of the model are as described in Section 7.3.1.5.

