7.3.1.5 Analysis

This secondary endpoint will be analyzed using the FAS. Following the treatment policy estimand all data will be included in the analysis regardless of early treatment discontinuation or other intercurrent events.

A repeated measurements GLMM with the logit link function will be fitted with the secondary endpoint SRI-4 as dependent variable (from Month 1 to Month 6). The model will include the treatment group, month, the treatment group by month interaction, and the OCS and mSLEDAI-2K stratification variables (from IXRS) as fixed effects.

An unstructured (UN) covariance structure will be used for estimation of the correlation between responses measured within the same subjects across multiple months. If this analysis fails to converge, the following structures will be tested in a subsequent order until model-convergence is achieved: heterogeneous Toeplitz (TOEPH); Toeplitz (TOEP); autoregressive (AR(1)); compound symmetry (CS).

Parameters will be estimated using restricted pseudo-likelihood with Newton Raphson ridging optimization and the Kenward-Roger method for calculating the denominator degrees of freedom.

The study treatment groups will be compared against placebo at each month using ORs and 95% CIs. The main comparisons are at Month 6.

The analysis will be implemented by the following SAS[®] code:

```
proc glimmix;
  nloptions technique=nrridg;
  class subjid ocs sledai_sc treatment month;
  model response = ocs sledai_sc treatment month treatment*month / link=logit dist=bin
  ddfm=kr;
  random month / type=un subject=subjid rside;
  lsmeans treatment*month / ilink cl; /* estimates event rates */
  lsmeans treatment*month / oddsratio diff cl; /* estimates ORs */
run;
```

Data for this endpoint will be summarized descriptively and listed using the FAS.

7.3.1.6 *Supplementary/sensitivity analyses*

7.3.1.6.1 *Analyses based on PPS*

The analysis of the secondary endpoint will be repeated using the PPS.

7.3.1.6.2 *Multiple imputation under MAR*

7.3.1.6.2.1 Step 1 (imputation)

Missing monthly SRI-4 scores will be imputed using a multiple imputation method [Rubin 1987], based on a model including the treatment group, the stratification factors OCS and mSLEDAI-2K (from IXRS), and all post-baseline monthly scores up to Month 6.

Instead of imputing a single value for each missing observation, a set of values is generated from the model, resulting in as many distinct complete datasets without missing data.

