7.5.6.2 Analysis

Group 1

The analysis will be based on an MMRM model, similar to the one used for the primary analysis [Section 7.2.5] based on 5 treatment groups as described in Section 5.4.3.3.

Group 2

The analysis will be based on an MMRM model, similar to the one used for the primary analysis [Section 7.2.5]. The model will be fitted including data from Month 7 up to Month 12 and from treatment groups *Cenerimod 2 mg / Ex-4 mg* and *Placebo / Ex-4 mg*. The model will include treatment group, month, TP2 baseline PGA score, treatment group by month interaction and TP2 baseline PGA score by month interaction as fixed effects.

All other aspects of the model are as described in Section 7.2.5.

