7.5.8.2 Analysis

Group 1

A Cox proportional hazards model will be performed as described in Section [7.4.5.2](#) based on 5 treatment groups as described in Section [5.4.3.3](#) for data up to EOT and up to Month 12.

Group 2

A Cox proportional hazards model will be performed with treatment as a factor, only including treatment groups *Cenerimod 2 mg / Ex-4 mg* and *Placebo / Ex-4 mg*.

7.5.9 Time to first flare from baseline to Month 12

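### The Group 2 SRI-4 model leaves out TP2 baseline mSLEDAI-2K, although the Group 2 model for its mSLEDAI-2K component adjusts for it; the likely loss of efficiency is small

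*SAP*

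**What the plan says.** SAP 7.5.5.2 fits the Group 2 SRI endpoints with a repeated-measures GLMM on Months 7 to 12 in the two ex-4 mg arms. Its fixed effects are: "The model will include treatment group, month and treatment group by month interaction as fixed effects". It then adds: "All other aspects of the model are as described in Section 7.3.1.5".

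The parent model in SAP 7.3.1.5 has "the treatment group by month interaction, and the OCS and mSLEDAI-2K stratification variables (from IXRS) as fixed effects" besides treatment and month. The natural reading is that the Group 2 list replaces that list. On either reading, no TP2 baseline value enters.

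SAP 7.5.3.2 uses the same GLMM, arms and months for mSLEDAI-2K response, and includes "treatment group, month, TP2 baseline mSLEDAI-2K score, treatment group by month interaction and TP2 baseline mSLEDAI-2K score by month interaction as fixed effects". The Group 2 models for mSLEDAI-2K change (7.5.2.2) and PGA change (7.5.6.2) also carry their TP2 baseline and its interaction with month.

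SRI-4 (SAP 7.1 and 7.3.1.2) requires a fall of at least 4 points in mSLEDAI-2K together with a BILAG and a PGA condition. SAP 7.4.3.1, which 7.5.5.1 carries into Group 2, leaves out subjects whose baseline is below X for SRI-X with X from 5 to 8. No such rule is given for SRI-4. The SAP does not explain why 7.5.3.2 and 7.5.5.2 differ.

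**The concern.** The mSLEDAI-2K component is adjusted for TP2 baseline, while the composite that contains it is not. TP2 baseline is measured at Month 6, after six months on 4 mg, so some low scores are plausible. Subjects scoring below 4 stay in the SRI-4 model as certain non-responders and dilute both arms.

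The effect of dose reduction or withdrawal after 4 mg is a stated exploratory objective (SAP 3.3) and rests on about 30 subjects per arm. In so small a comparison, leaving out a covariate that is already derived and is linked to the outcome gives up some efficiency. It also means that the SRI-4 odds ratio is not conditional on baseline while the mSLEDAI-2K response odds ratio is.

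**Working it through.** **No figure to reproduce.** The SAP states no power, effect size or response rate for Group 2. Response rates, baseline distributions and covariate strength below are assumptions.

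**Arm size.** SAP 2.1 gives 325 subjects in five equal arms: 325 / 5 = 65 on 4 mg. Re-randomization is 1:1 among those still on 4 mg at Month 6: 65 / 2 = 32.5 per arm at most. The 6% expected missing at Month 6 (SAP 7.2.3) serves as a rough proxy for attrition: 32.5 × 0.94 = 30.5. At 10% attrition it is 29.2, and at 20% it is 26.0.

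**Link between baseline and response.** SAP 6.8.3.3.1 defines the score as a sum of weighted descriptors, so its minimum is 0. If B is the TP2 baseline and S ≥ 0 the later score, the reduction B − S is at most B. SRI-4 needs B − S ≥ 4, which is impossible when B < 4. If a share f of subjects has B < 4, the response rate in each arm is (1 − f) times the rate among the rest. With assumed rates of 30% and 65% among the rest:
- f = 20%: 0.8 × 30% = 24% against 0.8 × 65% = 52%.
- f = 40%: 0.6 × 30% = 18% against 0.6 × 65% = 39%.

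**Gain from a baseline main effect, first model.** Single-visit logistic regression, 30 per arm, likelihood-ratio test at nominal two-sided 5%, 4,000 simulated trials per setting, using the rates just given:

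| Share with B < 4 | Power, unadjusted | Power, adjusted | Null rejection, unadjusted / adjusted | Median OR, unadjusted / adjusted |
|---|---|---|---|---|
| 20% | 64% | 68% | 6.0% / 6.0% | 3.6 / 4.1 |
| 40% | 47% | 53% | 6.0% / 6.7% | 2.9 / 4.0 |

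**Second model.** TP2 baseline has mean 6 and SD 3.5. Month 12 score = 0.6 × baseline + 2.4 − effect + N(0, 2.6), rounded and floored at 0. Response is a fall of at least 4 points. At 30 per arm and nominal 5%, the gain is about 4 to 7 points. Both tests reject too often under the null, though: 6.6–7.8% unadjusted and 7.7–8.8% adjusted over 27 to 32 per arm. With critical values reset so that each test has 5% size, still at 30 per arm:
- effect of 2 points: about 38% to 39%;
- effect of 3 points: about 71% to 75%.

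That is a gain of about 1 to 5 points. The outcome is discrete, so this figure moves by a few points with arm size; it shows an order of magnitude only.

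**Limits of both models.** They use one visit, they omit the BILAG and PGA components of SRI-4, and they do not reproduce the pseudo-likelihood GLMM with Kenward-Roger degrees of freedom.

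**Parameter count.** Treatment by month uses 2 × 6 = 12 fixed effects. A baseline main effect makes 13. Adding baseline by month as well, as in 7.5.3.2, makes 12 + 1 + 5 = 18. The unstructured covariance has 6 × 7 / 2 = 21 more parameters, in about 60 subjects.

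**The case against.** The strongest reply is that nothing here is wrong. The comparison is randomized, so leaving out a baseline term causes no bias and does not invalidate the test, and the standard error already reflects chance imbalance. Group 2 is exploratory and outside the error-controlled family of SAP 7.1.1. A lean model is a reasonable choice in about 60 subjects, and the fallback in 7.3.1.5 simplifies only the covariance structure, not the fixed effects. Adjustment also changes the quantity reported: the conditional odds ratio lies further from 1 and has a larger standard error. All of this stands. It keeps the point small and argues against copying the month interaction from 7.5.3.2.

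A reader might infer more than the documents support:
- *That these models stand alone among the Group 2 models.* The Group 2 time-to-flare models also lack a baseline term: "A Cox proportional hazards model will be performed with treatment as a factor, only including treatment groups" the two ex-4 mg arms (7.5.8.2, and likewise 7.5.9.2).
- *That dropping the IXRS stratification factors is a fault.* The fixed-effect lists in 7.5.2.2, 7.5.3.2 and 7.5.6.2 omit them too, and no stratification is stated for the re-randomization.
- *That the point covers SRI-5 to SRI-8.* The exclusion rule in 7.4.3.1 already removes subjects who cannot respond, and the smaller numbers left would make added terms hard to support.
- *That it covers the BILAG response in 7.5.4.2.* That model has the same short list, but no calculation shows a loss of power there.
- *That the gain is 6 to 9 power points.* The second model can give this at nominal 5% with 27 to 32 per arm, but it then compares two tests of unequal size, both above 5%, on wholly assumed inputs.

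**Conclusion.** The point holds for SRI-4 only. The Group 2 SRI-4 model omits a covariate that the SAP already uses for the mSLEDAI-2K component of the same endpoint and that limits who can respond. The expected benefit of including it is small: about 1 to 5 power points at equal Type I error, with 30 per arm and the assumed distributions above.

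The gain depends on how many subjects have a TP2 baseline below 4 and, more generally, on how strongly baseline predicts response. The documents give neither. If baseline did not predict response the gain would be nil, but that is unlikely for SRI-4 given how the endpoint is built. The planned analysis is neither biased nor invalid. This is a minor, worthwhile refinement of an exploratory analysis.

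**What to change.** In SAP 7.5.5.2, Group 2, add a sentence for SRI-4 only: the model also includes the continuous TP2 baseline mSLEDAI-2K score as a fixed main effect. No baseline-by-month term is needed. If the sponsor prefers to leave it out, one line giving the reason would do.

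The cost is one more parameter (13 fixed effects in place of 12). TP2 baseline is already defined in SAP 5.2, so no new derivation is needed. The SRI-4 odds ratio becomes conditional on TP2 baseline, as the mSLEDAI-2K response odds ratio in 7.5.3.2 already is, and the table footnote should say so.

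Under SAP 2.1 one sponsor team is unblinded at the Month-6 analysis. The change should therefore be made without sight of TP2 results by arm. If those have already been seen, report the adjusted model as a labelled supplementary analysis beside the planned one.
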